Specifically after triage and senior clinical assessment at each of the acute EMBER sites (CDU, DDU, CAU) if a primary clinical diagnosis of (i) exacerbation of heart failure, ii) exacerbation of asthma/COPD, (iii) adult community acquired pneumonia or (iv) paediatric exacerbations of acute childhood wheeze and confirmed asthma has been made, members of the EMBER research team will evaluate patients using breath diagnosis and sensing technologies and additional tools to characterise patients that are acutely unwell.

The following steps will be employed at all sites:

- 1) Identify patients with acute breathlessness defined as one or more of (i) patient defined acute breathlessness and/or a (ii) 1 unit increase in (eMRC)
 - 2) Completeion of study diagnosis at the point of senior clinical decision maker review
 - 3) Informed consent

Page 17 of 46

- 4) In selected patients that have not been captured during their acute admission and have been discharged prior to EMBER assessments (for example patients that may have been discharged rapidly due to the use of an ambulatory care pathway), *recall within 48 hours of discharge* will be performed for EMBER assessments
- 5) Breath sampling using a standardised CE marked multi-platform breath sampling face mask as well as real time breath sampling.
- 6) Collection of additional biomarkers for future biomarker discovery campaigns Including a (i) urine sample, (ii) blood sample (up to 85 mls) (DNA, RNA ,plasma and serum), peripheral blood cell flow cytometry and (iii) spontaneous sputum samples (plugs and supernatants). These samples will be collected at time point 1a/1b and at 2
- 1) Stable state follow up of all patients will occur following recovery from the acute event. Assessment will occur at time of clinical follow up, or as a separate research visit.

The expected duration of participants within the study will therefore be equivalent to their length of hospital stay and up to the stable state follow up visit, with a similar duration for healthy volunteers and stable state patients.

Readmission to hospital within the protocol defined recovery period. Patients that re admit to hospital between visits 1 and 2, can have additional $1a\pm1b$ assessments. Visit 2 will be taken as recovery following the subsequent admission. If a patient is admitted to hospital after visit 2 then they will be eligible to be recruited as a new study participant.

Definition of Acute Breatlessness

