9.1.5 Expected Serious Adverse Events/Reactions

The patient cohort being studied are frail and have a high hospital readmission rate and mortality rate. For example in those with a diagnosis of COPD both national and local data suggest readmission to hospital will be 20% at one month, 33% at 3 months and 60% at one year. A number of these patients will be readmitted on more than one occasion (our study Greening N et al, BMJ 2014) demonstrated 599 hospitalisations in one year in a similar COPD population of 389. In addition mortality is expected to be 14% at 3 months and 20% at one year.

Given this is an observational study and the rates that are expected we would reasonably expect that hospitalisation or death are not routinely reported as SAEs (we would anticipated an excess of 600 SAEs if not). Therefore expected serious adverse events include (i) clinical deterioration and death of acutely breathless patients, (ii) adverse drug reactions to pharmacotherapy administered during the patients clinical care pathway, (iii) readmission to hospital for acute breathlessness due to acute exacerbations of comorbid conditions during the study period.

However, if any adverse events are experienced during any of the measures performed specifically related to research procedures (Table 1 and 2) e.g. breath sampling, administration of questionnaires, then these will be reported using the approved reporting procedure.

Page 31 of 46

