10. STATISTICS

participants.

10.1 Description of Statistical Methods (Detailed statistical anad analytical methods are outlined in the MRC-EMBER data analysis plan).

Primary Analysis

For the primary analysis the outcome is a nominal variable with levels (1) Acute breathlessness (2) Recovery form acute breathlessness. The relationship between the primary outcome and the metabolomics biomarkers in exhaled breath sample will be modelled using multinomial logistic regression. Acute

Page 32 of 46

breathlessness will be defined as one or more of (i) patient defined acute breathlessness and/or a (ii) 1 unit increase in Extended Medical Research Council breathlessness score (eMRC). In addition to metabolomics markers the following independent variables will be included in the model: age, sex, standard acute care pathology markers blood eosinophils, BNP, CRP, Troponin-I, canonical VOCs extracted from breath analysis and where relevant validated co morbidity scores (e.g. Charlson comorbidity score).

Adjudication

All acute/healthy adult patients' notes will be sequentially divided. These will then be reviewed and independently adjudicated by two independent respiratory consultants, blinded to admission bloods and diagnosis. The panel will independantly decide the primary diagnosis as well as mark their level of certainty on a 100 mm VAS scale. The panel member will then be able to review imaging, ECGs, and ABGs but not blood results. Results will be both -validated by separate panel member to ensure agreement using Bland-Altman and Correlations and within rater agreement will be assessed by replicate analysis of at least 20 cases 4 weeks apart.

Binary logistic regressions will be utilised to assess associations between VOCs and acute disease. ROC curves will be produced for individual predictors in the primary analysis. Additional techniques for multi variate analysis including but not limited to cluster analysis, structural equation modelling and topological data analyses will be applied where relevant. Tables of descriptive statistics will be compiled for all key variables. All analysis will be performed using SAS 9.4 http://www.r-project.org/.

Secondary Analysis

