For the secondary analysis pertaining to other definitions of acute breathlessness, visual analogue breathlessness scores (100mm) and a 1 unit increase in the extended medical research council analysis outlined above for the primary endpoint will be performed based upon stratification of breathlessness type.

For the secondary analyses pertaining to discovery of breath metabolomics markers the outcome is a nominal variable with levels (1) Acute Heart failure (2) Community acquired pneumonia 3) Adult exacerbations of asthma/COPD (both in combination and considered individually) and (4) Acute exacerbations childhood wheeze and confirmed asthma in children. The relationship between the primary outcome and the metabolomics biomarkers in exhaled breath sample will be modelled using multinomial logistic regression and ROC curves. In addition to metabolomics markers the following independent variables will be included in the models where necessary (improve model fit): age, sex, validated co morbidity scores such as the Charlson score, indicator disease risk scores such as the CURB-65 pneumonia score, DECAF COPD exacerbation scores and treatments commonly used acutely for the indicator diagnoses.

Subsidiary Analysis

For subsidiary analyses modelling risk of re admission, death and length of stay we will utilise the following approaches

- Cox proportional hazards model will be fitted and competing risk models will be fitted for readmission. Logistic regression analysis will be used when looking at risk at particular time points for readmission.
- The number of exacerbation events will be modelled using Poisson or Negative Binomial regression.
- Relationship between death and breath biomarkers will be evaluated using a logistic regression model.

Page 33 of 46

For subsidiary analyses pertaining to dynamic profile of breath biomarkers during (i) the acute states (time points 1a), (ii) transition to the stable state (time point 1b) and (iii) in the chronic state 8-12 weeks post exacerbation (time point 2), a repeated measures model with a random intercept and random effect for time will be fitted, the random effects will be fitted for each patient. For the repeated measures mixed model an unstructured covariance will be assumed.

Other outcomes are exploratory and based around feasibility of an acute care platform for airways disease. Statistical analyses for these outcomes will be performed as appropriate for hypotheses derived in this exploration.

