10.2 The Number of Participants

The sample size for the study is based on the requirements of the multinomial logistic regression model for the primary analysis. We estimate that if the number of events to number of variables in the model is in the ratio 20:1 a sufficiently large sample size will be obtained [24]. We regard this study as being exploratory it will serve as a basis for determining the sample size required for a larger study in the future. (Appendix D)

- 10.3 The Level of Statistical Significance
- All tests will be performed at the 5% significance level.
- 10.4 Criteria for the Termination of the Trial. Last participant, last visit
 - 10.5 Procedure for Accounting for Missing, Unused, and Spurious Data. Describe

A table listing all key variables with percentage of missing data will be reported and where possible the reason for missing data will be reported. Missing data will be imputed using PROC MI in SAS. Spurious data will be reported and where possible correct values will be inserted, if it is not possible to supply correct values value will be deleted.

10.6 Procedures for Reporting any Deviation(s) from the Original Statistical Plan An interim sample size calculation will be performed at the end of the discovery phase (Quarter 2, year 3) of the project; this calculation will identify the optimal number of patients in each replication phase disease indicator group based upon the optimal number of metabolomic biomarkers associated with the disease and the key outcome data from the discovery phase e.g. risk prediction, 30 / 60 day re admissions, discrimination of disease state from healthy state.

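### The primary acute-versus-recovery model has no patient term although most patients supply both samples, and the protocol does not fix which acute sample pairs with visit 2 after a readmission or how deaths before visit 2 are treated

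*Protocol*

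**What the plan says.** **Outcome and model.** Section 10.1 states that for the primary analysis "the outcome is a nominal variable with levels (1) Acute breathlessness (2) Recovery form acute breathlessness", and that the "metabolomics biomarkers in exhaled breath sample will be modelled using multinomial logistic regression". Age, sex, blood markers and, where relevant, comorbidity scores are listed as covariates. No patient effect, stratum or clustering is named. Section 6.1 defines recovery in the acute patients themselves: patient- or clinician-reported recovery, at least 6 weeks and up to 6 months after the event.

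**Patient-level modelling elsewhere.** For the subsidiary analysis of dynamic profiles, 10.1 says that "a repeated measures model with a random intercept and random effect for time will be fitted", with random effects for each patient.

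**Readmission.** Section 6.1 says "Patients that re admit to hospital between visits 1 and 2, can have additional" 1a and, if wanted, 1b assessments, and then "Visit 2 will be taken as recovery following the subsequent admission". A patient admitted after visit 2 may be enrolled again as a new participant.

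**Deaths and missing data.** Section 9.1.5 takes COPD as its example, with readmission of 20% at one month and 33% at 3 months, and continues: "In addition mortality is expected to be 14% at 3 months and 20% at one year". Section 10.5 says "Missing data will be imputed using PROC MI in SAS" and makes no exception for death. Section 10.7 includes all eligible consented participants.

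**The concern.** Three features of the primary contrast do not fit together.

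1. The two outcome levels are mostly two samples from the same patient, but the named model treats each sample as a separate observation. Its standard errors are then wrong for the contrast.
2. After a readmission, the recovery sample is reassigned to the later admission and the acute sample is not. If the optional repeat 1a is skipped, visit 2 has no acute sample from its own episode. If it is taken, the patient has two acute samples and no rule selects one.
3. The acute level contains everyone sampled; the recovery level contains only those who survive and return. A marker that is constantly higher in patients with a poor prognosis, with no acute change at all, would differ between the levels.

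At stake are the power of the primary test and whether a modest association can be read as a marker of acute breathlessness rather than of prognosis.

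**Working it through.** **The plan's own figures.** Section 21.3 uses N_spec = z² × Sp × (1 − Sp) / (d² × (1 − prevalence)). With 1.96² × 0.8 × 0.2 / (0.08² × 0.2) this is 480.2, against the stated 480. The figure reproduces, but its comparator is the healthy controls (1 in 5 recruited), not recovery samples. The sample-size figures therefore do not address this contrast and make no allowance for loss before visit 2.

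**A. Effect of ignoring the pairing.**
Inputs: 220 pairs (four acute adult classes × 55 in one phase, section 21.5) and a 5% two-sided test (10.3). Assumed: correlation 0.5, marker SD 1, and a shift of 0.18 SD (ln 1.2 = 0.18, reading the odds ratio in 21.2 as per SD, a unit the protocol does not state).
- Standard error assumed by the unpaired model: √(2/220) = 0.0953. It rejects when the difference exceeds 1.96 × 0.0953 = 0.187.
- True standard error: √(2 × (1 − 0.5)/220) = 0.0674.
- Type I error: 2 × P(Z > 0.187/0.0674) = 2 × P(Z > 2.77) = 0.6%.
- Power, unpaired: P(Z > (0.187 − 0.18)/0.0674) = P(Z > 0.10) = 46%.
- Power, paired: P(Z > 1.96 − 0.18/0.0674) = P(Z > −0.71) = 76%.

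Simulation of the logistic models agrees: about 44% unpaired and about 77% with pairing or clustering, and type I error about 1%. In a repeat of 1,000 runs, patient-clustered standard errors and conditional logistic regression each gave 74% power, with type I error of 4.5% and 4.6%. By the same formulae, a correlation of 0.3 gives type I error 1.9% and power of 47% unpaired against 62% paired. At 0.7 they are 0.03%, 45% and 93%.

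**B. Readmission.** On the COPD rates, 55 × 0.20 = 11 patients are readmitted by one month and 55 × 0.33 ≈ 18 by 3 months, the latter inside the 6-week to 6-month window. Each is a possible episode mismatch, not a certain one. The protocol gives nothing from which to compute the resulting bias.

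**C. Deaths before visit 2.** On the COPD rate, 55 × 0.14 = 7.7, about 8 patients. Assume that those who die carry a marker k SD higher at all times, with no acute change in anyone, and that they have no recovery sample. With a proportion p dead, the acute mean exceeds the recovery mean by p × k. The log odds ratio per SD is about p × k divided by the average variance of the two groups, (2 + p(1 − p)k²)/2.

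| Deaths before visit 2 | k = 0.5 | k = 1 |
|---|---|---|
| 14% in all strata | OR 1.07 | OR 1.14 |
| COPD only, 7.7/220 = 3.5% | OR 1.02 | OR 1.04 |

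Worked case: p = 0.14, k = 1 gives 0.14/1.06 = 0.132, OR 1.14. Simulation gives the same table.

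**D. If the dead are imputed.** With correlation 0.5, imputing visit 2 from 1a moves the imputed mean about half of k upwards. At 14% and k = 1 the spurious difference falls from 0.14 to 0.14 × 0.5 = 0.07, OR about 1.07. At k = 0.5 it is 0.035, OR about 1.03 to 1.04. Imputation thus reduces this bias, but it does so by inventing a recovery profile for people who never recovered.

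**The case against.** **Details are referred to a separate data analysis plan, not shown, which may specify clustering, pairing and the scope of imputation.** That may be so, and the point is limited to what the protocol fixes. But the model, the reassignment of visit 2, the optional repeat 1a and the general imputation rule are all stated in the protocol.

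**A diagnostic test is read without the patient's own recovery sample, so a between-sample model is legitimate.** This stands. The primary objective is sensitivity, specificity and predictive values. Conditional logistic regression gives no absolute predicted probability, and the main effect of sex (and in practice age) drops out. It cannot serve alone as the primary model.

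**The study is called exploratory and the error is conservative.** This stands, and it limits the severity.

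Stronger readings that a reader might infer, and that the documents do not support:
- *Acute and recovery samples come from different people.* They come from the same people; the recovery level is the surviving, returning subset. Readmitted patients still contribute a visit 2.
- *Ignoring the pairing inflates false positives.* With one sample per level per patient it does the opposite, and separate intervals for sensitivity and specificity are unaffected.
- *14% and 33% apply throughout.* The rates follow a COPD example. Exclusion (iv) also allows patients with poor prognosis to be left out, and since visit 2 can fall from 6 weeks, not every 3-month event precedes it.
- *A spurious 1.14 nearly reaches the target of 1.2.* That target has no stated unit and was derived for other comparators. The 1.14 also omits the covariate adjustment in 10.1.
- *Selective loss and imputation of the dead both add to the bias.* They are alternatives. Moreover, 10.5 permits imputing visit 2 after death without saying that it will be done, and the definition of recovery in 6.1 cannot be met by a patient who has died.

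**Conclusion.** The point holds as a should-fix. As written, the primary model ignores that most patients supply both outcome levels. With 220 complete pairs, correlation 0.5 and a 0.18 SD shift, this costs roughly 30 percentage points of power (about 44% against 77%) and lowers type I error to about 1%. The size depends on the correlation, which the protocol does not give.

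The pairing of visit 2 with an acute sample after readmission is undefined, and an index 1a can meet recovery from another episode. How often depends on how often the optional 1a is repeated.

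Selective loss through death can create a modest spurious association: OR about 1.02 to 1.14 per SD under assumed marker differences of 0.5 to 1 SD. The upper end requires all strata to share the COPD example's mortality. None of this makes the acute-recovery contrast unusable.

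**What to change.** - **10.1:** state that the primary model accounts for repeated samples from the same person, by patient-clustered robust standard errors or GEE. Predicted probabilities, ROC curves, sensitivity and specificity are kept, with patient-clustered intervals. Cluster on the person, since 6.1 allows re-enrolment under a new participation.
- **10.1:** add a within-patient analysis (conditional logistic regression) restricted to patients with both samples, as the check against selective loss.
- **6.1:** state that visit 2 is paired with the 1a of the admission it follows, and that a readmitted patient without that 1a does not form a pair.
- **10.5:** state that visit 2 breath data are not imputed for patients who died before it.

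The cost is wording in three sections, with no extra patients or visits. There will be fewer pairs, and the paired estimate applies to patients who recover. On the COPD rate, 55 patients leave about 47 alive at 3 months; keeping 55 would need 55/0.86 = 64 patients. That is a figure to report alongside the result, not a required increase.

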	Discovery Phase (years 1-2): Acute Heart failure (n=55-100), Community acquired pneumonia (n=55-100), adult exacerbations of asthma and COPD (n=110-200), paediatric exacerbations of acute childhoodwheeze and/or confirmed asthma (n=50-100), Age/Home environment matched Adult/Sibling/Parent/Spousal healthy volunteers (n=55-150 adults/50 children)
	Replication Phase (years 3-4): Acute Heart failure (n=55-100), Community acquired pneumonia (n=55-100), adult exacerbations of asthma and COPD (n=110-200), paediatric exacerbations of acute childhood wheeze and/or confirmed asthma (n=25-50), Age/Home environment matched Adult/Sibling/Parent/Spousal healthy volunteers (n=55-75 adult/25 children)
	Additional patients with stable COPD/Asthma/Heart failure n=200 Total Sample Size = 550-1250 patients.
Follow-up duration	Acute care participants will have up to 2 visits whilst an inpatient followed by a 'Post-Acute Event Recovery' at a minimum of 6 weeks post discharge and up to 6 months. Stable state participants and healthy volunteers will have 2 visits over 16 weeks. All participants will have outcome data 2 years post recruitment.
Planned Trial Period	3 years
Primary Objective	To evaluate the sensitivity, specificity, positive and negative predictive value of metabolomic biomarkers in exhaled breath samples to identify acute breathlessness, defined as one or more of (i) patient defined acute breathlessness and/or a (ii) 1 unit increase in Extended Medical Research Council breathlessness score (eMRC).
Secondary Objectives	To replicate selected metabolomic breath biomarker panels of acute breathlessness using a combination of both (i) discovery technologies (including GC-MS) and (ii) point of care auto tuned breath sensing devices (including linear IMS, CMS, PTR-MS).
	2) To evaluate the primary endpoint stratified by breathlessness as follows (i) change in eMRC by 1 unit, (ii) patient defined breathlessness and (iii) 100 mm visual analogue score for breathlessness
	To discover and replicate metabolomic breath biomarkers that differentiate (i) Acute Heart failure, (ii) Community acquired pneumonia, (iii) Adult exacerbations of asthma and COPD

	To quantify the level of clinical uncertainty in the primary diagnosis using a 100 mm visual analogue scale and independent clinical adjudication of case notes blinded to the following blood biomarkers (i) CRP (ii) blood eosinophils (iii) BNP (iv) Troponin-I but not clinical history and chest X-ray.

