5.2 Secondary Objectives

- To replicate selected metabolomic breath biomarker panels of acute breathlessness using a combination of both (i) discovery technologies (including GC-MS) and (ii) point of care auto tuned breath sensing devices (including linear IMS, CMS, PTR-MS).
- To evaluate the primary endpoint stratified by breathlessness as follows (i) change in eMRC by 1
 unit, (ii) patient defined breathlessness and (iii) 100 mm visual analogue score for breathlessness
- To discover and replicate metabolomic breath biomarkers that differentiate (i) Acute Heart failure,
 (ii) Community acquired pneumonia, (iii) Adult exacerbations of asthma and COPD
- To quantify the level of clinical uncertainty in the primary diagnosis using a 100 mm visual analogue scale and independent clinical adjudication of case notes blinded to the following blood biomarkers (i) CRP (ii) blood eosinophils (iii) BNP (iv) Troponin-I but not clinical history and chest X-ray.
- To identify and discover metabolomic breath biomarkers of acute childhood wheeze and or confimed asthma.

To clinically validate metabolomic breath biomarkers generated above using a combination of existing pathology markers e.g. BNP, CRP, blood eosinophils and troponin- I and other clinical relevant prognostic scoring tools e.g DECAF, CURB65 and Heart failure risk calculator http://www.heartfailurerisk.org/^[19]

- Replication of acute breathlessness biomarkers will be according to the following predefined primary diagnoses in the replication phase:
 - (i) Acute Heart failure (n=55-100),(ii) Community acquired pneumonia (n=55-100), (iii) adult exacerbations of asthma and COPD (n=110-200),(iv) paediatric exacerbations of acute childhood wheeze and confirmed asthma (n=25-100),(v) age/home environment matched adult/spouse/sibling/parent control subjects (n=55-75 adults/25 children)
 - 5.3 Exploratory End Points (where applicable)
 - 1) To evaluate the dynamic profile of breath biomarkers during (i) the acute state, (ii) in the recovery state post exacerbation.

Page 15 of 46

- 2) To evaluate the relationship between breath metabolomic biomarkers and health status/ functional measures:
- Health status measures
- Physical performance
 - 3) To evaluate the relationship between metabolomic breath biomarkers and clinical outcomes including (i) hospital readmission at time points up to 2 years (ii) response to standard clinical therapy and (iii) death.

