A standard definition for acute breathlessness does not exist. We will use the presence of patient reported acute breathlessness, above their usual baseline breathlessness (i.e. in stable state) as a binary variable. We will also use the extended MRC score, and 100mm visual analogue score (VAS), as a continuous variable.

The extended MRC score has been validated in chronic disease populations, including in the acute state, and may be applied to diseases other than COPD where originaly validated. We will define a change in breathlessness of the eMRC as at least a unit change from stable state. In addition a VAS score will be used to measure breathlessness.

Definition of Post Exacerbation Recovery

Patient recovery will be defined as

- (i) Patient reported recovery from the acute exacerbation spell and back to their baseline extended MRC score or clinician defined recovery from the acute exacerbation spell and
- (ii) At least 6 weeks post exacerbation event (up to 6 months).
 - 6.2 Summary of Additional Assessment and breath sampling procedures/ devices

A number of analytical devices will be utilised to sample breath in acutely ill patients and based upon the (i) clinical site, (ii) operational needs and likely patient grouping (severity of underlying condition at the point of admission) within each clinical site, (iii) balance of discovery and point of care sensing technologies: breath sensors will be co-located to the two EMBER acute admissions units. All devices will be maintained to a high level of operational readiness by the technicians and device specialists within the clinical operations group. All devices will be checked for safety by Medical Physics at University Hospitals of Leicester NHS Trust.

[figure not shown]
The following devices will be utilised to evaluate breath volatile organic compounds

Page 18 of 46

- A portable mass spectroscopy device (Advion Ltd) for discovery based metabolomic breath sampling. This device is also capable of real time sampling.
- A proton transfer mass spectroscopy device (PTRMS) for discovery based metabolomic breath sampling.
- A point of care GC-FAIMS Lonestar device (Owlstone Nanotech Ltd)
- A point of care linear IMS Bioscout device (Owlstone Ltd: GC-FAIMS Lonestar analyser)

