7 TRIAL PARTICIPANTS

7.1 Overall Description of Trial Participants

Each site will recruit patients with acute breathlessness. Final confirmation of the primary indicator diagnosis is usually available at discharge (following visit 1b) and after further diagnostics at the stable state follow up clinic (at visit 2). The final primary indicator diagnosis and additional comorbidities will be recorded at initial senior clinical review, discharge and at follow up. The indicator diagnosis will be used to define the number of patients recruited within each disease stratum.

The study will have two distinct phases:

Phase 1: Discovery of novel breath metabolomic biomarkers.

Phase 2: Replication and validation of selected biomarkers in Phase 1.

Planned recruitment to meet the primary, secondary and exploratory study endpoints is outlined below.

- (i) Acute Heart failure (n=55-100 Phase 1, n=55-100 phase 2)
- (ii) Adult community acquired pneumonia (n=55-100 Phase 1, n=55-10 Phase 2). This condition will be defined as new radiological consolidation responsive to treatment according to the British Thoracic Society (BTS) community acquired pneumonia guidelines.
- (iii) Adult exacerbations of airway diseases asthma and COPD (n=110-200 Phase 1, n=110-200 Phase 2). This condition will be defined as a clinician diagnosis with subsequent or historical evidence of objective diagnostic criteria according to national and international guidelines.
- (iv) Paediatric exacerbations of acute childhood wheeze and/or confirmed asthma (n=55-100 Phase 1, n=25-50 Phase 2).

This condition will be defined as a clinician diagnosis and for childhood wheeze/asthma subsequent or historical evidence of objective diagnostic criteria according to national and international guidelines.

(v) Age/environment matched Adult/spousal/parental/ sibling volunteers (n=55-150 adults/50 children) discovery phase, (n=55-75 adult/25 children)

replication phase) with no evidence or history of the indicator disease being evaluated in their spouse/sibling/child.

(vi) Stable state participants with a confirmed diagnosis of asthma, COPD or heart failure that have not had and exacerbation of their disease within the preceding 6 weeks (n=200 (100 in each phase)).

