10.7 Inclusion in Analysis

All eligible participants, that have provided informed consent and participated in either discovery or replication phase studies.

11.DIRECT ACCESS TO SOURCE DATA/DOCUMENTS

Direct access will be granted to authorised representatives from the sponsor, host institution and the regulatory authorities to permit trial-related monitoring, audits and inspections.

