21.7 Stable Disease Recruitment Plan

This should be opportunistic and support the following ongoing initiatives

- Mologics COPD study
- Mepolizumab severe asthma early response study
- [name] ACF: project April 2018 (small healthy volunteer repeatability study n=12 healthy adults baseline x2, 2 weeks, 3 months GC-MS ReCIVA, PTRMS ([name] to discuss at Exec).
- Severe asthma clinical patient samples if possible/samples from aligned BRC studies (agreed at the exec)

Planned acute study recruitment last patient visit 1a

1st Nov 2018 for combined discovery and replication

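### Section 6.1 allows re-enrolment after visit 2 and no rule keeps a person to one phase, so replication may include people whose samples helped select the markers

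*Protocol*

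**What the plan says.** Protocol section 6.1 covers two kinds of readmission. A patient readmitted between visits 1 and 2 stays in the same enrolment and can have extra acute assessments. For a later admission the rule is: "If a patient is admitted to hospital after visit 2 then they will be eligible to be recruited as a new study participant". No phase limit is attached. The definition of recovery in the same section places visit 2 between 6 weeks and 6 months after the event.

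Section 7.1 describes two distinct phases and gives the purpose of the second: "Phase 2: Replication and validation of selected biomarkers in Phase 1". It sets numbers per phase but does not assign a person to one phase. The inclusion and exclusion criteria (7.2, 7.3) address recent participation in a trial of an investigational product, but not earlier enrolment in this study. Section 10.7 defines who is analysed: "All eligible participants, that have provided informed consent and participated in either discovery or replication phase studies". The recruitment plan in Appendix C (21.5) lists 55 per adult class in each phase and has no rule for repeat enrolments.

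Section 9.1.5 expects readmission to be common in COPD: "readmission to hospital will be 20% at one month, 33% at 3 months and 60% at one year".

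**The concern.** Replication is informative because the people tested had no part in choosing the marker. If a discovery patient returns as a replication participant, that patient's stable features (diet, smoking, comorbidity, home environment, personal metabolism) can help select a marker by chance and then help confirm it. Replication becomes somewhat optimistic, and two records of one person may be counted as two independent observations.

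The change of instrument between phases does not fully remove the link. Section 5.2 plans replication "using a combination of both (i) discovery technologies (including GC-MS) and (ii) point of care auto tuned breath sensing devices", so GC-MS is used on both sides.

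Repeats may also be hard to see later. Section 14 makes the study number the research identifier, strips names, dates of birth, hospital and NHS numbers from research data, and restricts the link between study number and identity to authorised staff. A new participant would presumably receive a new number (an inference; the protocol does not say). The analyst could then be unable to recognise a repeat, whatever the analysis plan intends.

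**Working it through.** **Is there a rule that prevents overlap?** The places where one could stand are sections 6.1, 7.1, 7.2, 7.3, 10.1 to 10.7 and Appendix C. None contains one. The nearest is the either/or wording of 10.7, which describes the people included and excludes nobody.

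**The plan's own sample-size figures.** Appendix C (21.3) uses N = z² × p(1 − p) / (d² × prevalence). With z = 1.96, p = 0.8 and d = 0.08:
- Sensitivity: 3.8416 × 0.16 / (0.0064 × 0.8) = 120 (stated 120).
- Specificity: 3.8416 × 0.16 / (0.0064 × 0.2) = 480 (stated 480).

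Planned adult replication is 5 × 55 = 275, which is above 120 and below 480, as 21.4 says. Removing a few repeats does not change this. The issue is independence, not numbers.

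**How large could the overlap be? (COPD only; no other class has readmission figures)**
- First readmitted between 3 and 12 months (9.1.5, read as cumulative): 60% − 33% = 27%, or 0.27 × 55 = 14.9 of 55 discovery patients. Three months stands in for visit 2.
- Calendar: the Synopsis puts discovery in years 1-2 and replication in years 3-4. Assume uniform enrolment over 24 months and uniform readmission over months 3 to 12 (mean 7.5 months). The share of these readmissions falling after month 24 is 7.5/24 = 31%.
- Overlap: 0.27 × 0.3125 = 8.4%, or 4.6 of 55 places. This is before losses to death, a missed visit 2, a different diagnosis or refusal. Readmissions after 12 months and second readmissions are not counted.

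**What does that do to replication?** For a marker with no true effect, let Z1 and Z2 be the discovery and replication statistics, bivariate normal with correlation r. Then r = overlap × within-person correlation × share of the contrast's variance that comes from the overlapping group. The quantity of interest is P(Z2 > 1.96 | Z1 > 1.96), which is 2.50% under independence. The within-person correlation is assumed to be 0.3 to 0.8.

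| Contrast (replication sizes) | Variance share | r | False replication |
|---|---|---|---|
| COPD v healthy (55 v 55) | 0.5 | 0.013-0.034 | 2.7-3.0% |
| COPD v other acute classes (55 v 165) | 165/220 = 0.75 | 0.019-0.051 | 2.8-3.3% |
| All acute v healthy (220 v 55), only COPD overlapping | 0.2, overlap ÷ 4 | 0.001-0.003 | 2.5% |

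The primary contrast (section 10.1) is acute v recovery in the same people, so stable traits largely cancel. With an assumed correlation of 0 to 0.3 between a person's two acute-to-recovery changes, and COPD as a quarter of the acute adults, r is at most 0.084 × 0.3 / 4 = 0.006 and false replication is 2.5-2.6%.

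**Does the calendar hold?** Section 21.7 plans the last acute visit 1a for "1st Nov 2018 for combined discovery and replication", which does not fit replication in years 3-4. Even on this shorter timetable re-entry was possible. Appendix C reports 82 acute adults in the September 2017 interim analysis; with visit 2 at most 6 months after the event, about 7 months remained. Whether such re-entries would count as replication depends on when the phase changed, which the protocol does not settle.

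**The case against.** The strongest reply is that this belongs to the analysis plan. Section 10.1 refers detailed methods to a separate data analysis plan, and the construction of discovery and replication sets and the modelling of repeat records are often fixed there. That stands for the modelling. It does not stand for the recruitment rule, which this protocol fixes without a phase limit, or for the identifiability of repeats, which depends on the data flow in section 14.

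A second reply is that 7.1 speaks of distinct phases and 10.7 of one phase or the other, so disjoint sets are the natural reading. That reading is reasonable and may be what was meant, but neither sentence makes a returning patient ineligible for replication, while 6.1 expressly makes that patient eligible as a new participant.

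Third, the effect is small, replication is a secondary objective, and section 10.2 calls the study exploratory. All true, and it sets the weight of the point.

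Fourth, people with recurrent exacerbations belong to the population of a real-life acute study. That is fair: they need not be turned away. What matters is that they do not count as independent replication of markers they helped to choose.

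A reader might go further and infer that replication is in fact contaminated, or that a large part of the readmitted COPD patients will reappear in it. The documents do not support either. They record no repeat enrolment, give no re-recruitment rate and, on the years 1-2 / 3-4 calendar, place only about 31% of the 3 to 12 month readmissions in replication. A re-recruited share of one half (about 7 of 55) is beyond that window.

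**Conclusion.** The point holds as a cheap improvement, to be considered rather than required. The protocol permits a person to contribute to both marker selection and marker replication, and contains no text that prevents it. Whether this happens, and how often, cannot be derived from the documents.

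The illustration (up to about 5 of 55 COPD places; at most about 3.3% instead of 2.5% false replication in the worst contrast; close to 2.5% for the primary contrast) rests on assumed uniform enrolment and readmission, assumed within-person correlations, and the Synopsis calendar. It is neither a strict upper nor a strict lower bound, because later and second readmissions are left out while losses before re-recruitment are ignored. Confidence is medium: high that the rule is absent, low on the size.

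**What to change.** - In 6.1 and 10.7, state that a person belongs only to the phase of first enrolment, and is counted once in the replication test set and in the class target.
- Have the authorised holders of the identity link (section 14) supply a coded person flag with the research data, so that repeat enrolments are visible without disclosing identity.
- Report the number of repeat enrolments by class and phase.
- Leave the modelling of repeat records to the data analysis plan.

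The cost is one sentence in each of two sections and one coded field. The downside is that repeat enrolments no longer count towards the replication target. On the illustration above, that is a few of the 55 COPD places per phase in 21.5: 55 / (1 − 0.084) = 60 enrolments for 55 new people, about 5 more. The protocol gives a range only for asthma and COPD combined (110-200 per phase), and a few extra enrolments fit within it.
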